# 6.4. Completers, Retrieved Dropouts, Non-Retrieved Dropouts, and On Drug-Missing Endpoint Subjects

The methods of multiply imputing missing data require classifying subjects based on having evaluable measurements and their treatment status at the time of the endpoint (namely, Week 4 or Week 28). For the purpose of missing data imputation, the following types of subjects are defined in the table below.

Subject Classification	Description	
Completers	Subjects in the FAS who completed through the time of the endpoint (Week 4 or Week 28, as applicable) on study drug and have an evaluable measurement for that endpoint. For endpoints with more than one data component, the subject must have complete data for all components of the endpoint.	
Retrieved Dropouts	Subjects in the FAS who discontinue study drug prior to the time of the endpoint collection but remain in the study and have an evaluable measurement for that endpoint. For endpoints with more than one data component, the subject must have complete data for all components of the endpoint.	
Non-retrieved Dropouts	Non-retrieved dropouts are subjects in the FAS who discontinue from the study and from study drug and do not have an evaluable measurement for that endpoint.	
On Drug-Missing Endpoint	Subjects in the FAS who are on study drug at the time of the endpoint collection but do not have an evaluable measurement for that endpoint.	

Table 2: Evaluability of Subjects at Endpoint

## 6.5. Hormone Reference Ranges

The appropriate reference ranges for androstenedione will be assigned based on reference ranges provided in the lab manual for either sex and age (for Tanner stage 1) or sex and pubertal stage (for Tanner stages 2 to 5). These ranges are shown in Table 3. Reference ranges are also given by age for 17-OHP and by sex and age for testosterone.

The assignment of these hormone reference ranges will apply to all summaries and analyses that use reference ranges. DB period analyses will use the Tanner stage documented in the eCRF at Day 1. OL period analyses will use the Tanner stage documented in the eCRF at Week 28 or, if unavailable, the last tanner stage available prior to dosing in the OL period.

Lab Analyte	Reference Ranges: conventional units; SI units		
Serum 17-OHP	1-11 months: $\leq$ 147 ng/dL; $\leq$ 4.4541 nmol/L		
(conversion factor	1 year: $\leq 139 \text{ ng/dL}$ ; $\leq 4.2117 \text{ nmol/L}$		
nmol/L: x 0.0303)	2 years: $\leq 134 \text{ ng/dL}$ ; $\leq 4.0602 \text{ nmol/L}$		
,	3 years: $\leq 131 \text{ ng/dL}$ ; $\leq 3.9693 \text{ nmol/L}$		
	4 years: $\le 131 \text{ ng/dL}$ ; $\le 3.9693 \text{ nmol/L}$		
	5 years: $\le 133 \text{ ng/dL}$ ; $\le 4.0299 \text{ nmol/L}$		
	6 years: $\leq 137 \text{ ng/dL}$ ; $\leq 4.1511 \text{ nmol/L}$		
	7 years: $\le 145 \text{ ng/dL}$ ; $\le 4.3935 \text{ nmol/L}$		
	8 years: $\le 154 \text{ ng/dL}$ ; $\le 4.6662 \text{ nmol/L}$		
	9 years: $\le 166 \text{ ng/dL}$ ; $\le 5.0298 \text{ nmol/L}$		
	10 years: $\le 180 \text{ ng/dL}$ ; $\le 5.454 \text{ nmol/L}$		
	11 years: ≤ 196 ng/dL; ≤ 5.9388 nmol/L		
	12 years: $\leq 213 \text{ ng/dL}$ ; $\leq 6.4539 \text{ nmol/L}$		
	13 years: $\leq 233 \text{ ng/dL}$ ; $\leq 7.0599 \text{ nmol/L}$		
	14 years: $\le 254 \text{ ng/dL}$ ; $\le 7.6962 \text{ nmol/L}$		
	15 years: 19-276 ng/dL; 0.5757-8.3628 nmol/L		
	16 years: 23-300 ng/dL; 0.6969-9.09 nmol/L		
	17 years: 26-325 ng/dL; 0.7878-9.8475 nmol/L		
Serum	Females:		
Androstenedione	1-11 months: $\leq$ 41 ng/dL; $\leq$ 1.4309 nmol/L		
from ng/dL to	1 year: $\leq$ 35 ng/dL; $\leq$ 1.2215 nmol/L		
nmol/L: x 0.0349)	2 years: $\leq$ 34 ng/dL; $\leq$ 1.1866 nmol/L		
	3 years: $\leq$ 38 ng/dL; $\leq$ 1.3262 nmol/L		
	4 years: $\leq$ 42 ng/dL; $\leq$ 1.4658 nmol/L		
	5 years: $\leq$ 45 ng/dL; $\leq$ 1.5705 nmol/L		
	6 years: $\leq$ 45 ng/dL; $\leq$ 1.5705 nmol/L		
	7 years: $\leq$ 48 ng/dL; $\leq$ 1.6752 nmol/L		
	8 years: $\leq$ 57 ng/dL; $\leq$ 1.9893 nmol/L		
	9 years: $\leq$ 77 ng/dL; $\leq$ 2.6873 nmol/L		

Lab Analyte	Reference Ranges: conventional units; SI units
	10 years: 15-111 ng/dL; 0.5235-3.8739 nmol/L
	11 years: 24-149 ng/dL; 0.8376-5.2001 nmol/L
	12 years: 32-182 ng/dL; 1.1168-6.3518 nmol/L
	13 years: 37-205 ng/dL; 1.2913-7.1545 nmol/L
	14 years: 42-221 ng/dL; 1.4658-7.7129 nmol/L
	15 years: 46-238 ng/dL; 1.605-8.3062 nmol/L
	16 years: 50-252 ng/dL; 1.745-8.7948 nmol/L
	17 years: 53-265 ng/dL; 1.8497-9.2485 nmol/L
	Tanner Stages II-III: 43-180 ng/dL; 1.5007-6.282 nmol/L
	Tanner Stages IV-V: 73-220 ng/dL; 2.5477-7.6678 nmol/L
	Males:
	1-11 months: $\leq$ 41 ng/dL; $\leq$ 1.4309 nmol/L
	1 year: $\leq$ 31 ng/dL; $\leq$ 1.0819 nmol/L
	2 years: $\leq 27 \text{ ng/dL}$ ; $\leq 0.9423 \text{ nmol/L}$
	3 years: $\leq 27 \text{ ng/dL}$ ; $\leq 0.9423 \text{ nmol/L}$
	4 years: $\leq 29 \text{ ng/dL}$ ; $\leq 1.0121 \text{ nmol/L}$
	5 years: $\leq$ 31 ng/dL; $\leq$ 1.0819 nmol/L
	6 years: $\leq$ 36 ng/dL; $\leq$ 1.2564 nmol/L
	7 years: $\leq$ 43 ng/dL; $\leq$ 1.5007 nmol/L
	8 years: $\leq$ 54 ng/dL; $\leq$ 1.8846 nmol/L
	9 years: $\leq$ 65 ng/dL; $\leq$ 2.2685 nmol/L
	10 years: 10-77 ng/dL; 0.349-2.6873 nmol/L
	11 years: 12-90 ng/dL; 0.4188-3.141 nmol/L
	12 years: 14-106 ng/dL; 0.4886-3.6994 nmol/L
	13 years: 17-124 ng/dL; 0.5933-4.3276 nmol/L
	14 years: 19-139 ng/dL; 0.6631-4.8511 nmol/L
	15 years: 21-154 ng/dL; 0.7329-5.3746 nmol/L
	16 years: 24-172 ng/dL; 0.8376-6.0028 nmol/L
	17 years: 27-192 ng/dL; 0.9423-6.7008 nmol/L
	Tanner Stages II-III: 17-82 ng/dL; 0.5933-2.8618 nmol/L
	Tanner Stages IV-V: 57-150 ng/dL; 1.9893-5.235 nmol/L

Lab Analyte	Reference Ranges: conventional units; SI units
Serum Testosterone (conversion factor from ng/dL to nmol/L: x 0.0347)	Females: 1-<6 years: $\leq 8 \text{ ng/dL}$ ; $\leq 0.2776 \text{ nmol/L}$ 6-<8 years: $\leq 20 \text{ ng/dL}$ ; $\leq 0.694 \text{ nmol/L}$ 8-<11 years: $\leq 35 \text{ ng/dL}$ ; $\leq 1.2145 \text{ nmol/L}$ 11-<12 years: $\leq 40 \text{ ng/dL}$ ; $\leq 1.388 \text{ nmol/L}$
	$12 - <14$ years: $\le 40$ ng/dL; $\le 1.388$ nmol/L 14-17 years: $\le 40$ ng/dL; $\le 1.388$ nmol/L
	Males: 1-<6 years: $\leq 5 \text{ ng/dL}$ ; $\leq 0.1735 \text{ nmol/L}$ 6-<8 years: $\leq 25 \text{ ng/dL}$ ; $\leq 0.8675 \text{ nmol/L}$ 8-<11 years: $\leq 42 \text{ ng/dL}$ ; $\leq 1.4574 \text{ nmol/L}$ 11-<12 years: $\leq 260 \text{ ng/dL}$ ; $\leq 9.022 \text{ nmol/L}$ 12- <14 years: $\leq 420 \text{ ng/dL}$ ; $\leq 14.574 \text{ nmol/L}$ 14-17 years: $\leq 1000 \text{ ng/dL}$ ; $\leq 34.7 \text{ nmol/L}$

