## 4.2. Key Secondary Efficacy – DB Period

Key secondary efficacy endpoints in the DB period are:

- Change from baseline in serum 17-hydroxyprogesterone (17-OHP) at Week 4
- Percent change from baseline in glucocorticoid daily dose (in hydrocortisone equivalents adjusted for BSA [mg/m^2/day]) at Week 28, while Week 28 serum androstenedione is ≤120% of the baseline value or ≤ ULN, according to sex and either age (for Tanner stage 1) or pubertal stage (for Tanner stages 2 to 5)

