The second key secondary endpoint of percent change from baseline in glucocorticoid daily dose at Week 28 is based on the glucocorticoid concomitant medications eCRF. The method of collecting concomitant medication data involves entering a start date and stop date for each medication, unless it is ongoing, in which case the "Ongoing?" field is marked as "yes." This differs from assessments that are collected discretely at visits. Additionally, the androstenedione values collected at the Week 28 visit are a critical component to the assessment of this endpoint as subjects who do not maintain androstenedione control and have a decrease from baseline in glucocorticoid total daily dose will have their percent change from baseline value in glucocorticoid total daily dose set to 0. For the purposes of determining the glucocorticoid total daily dose from the eCRF at Week 28, the Week 28 visit date at which the androstenedione values were collected (based on the analysis visit mapping described below) will be used to determine the glucocorticoid dose (as of the same date) to be used for the second key secondary endpoint. If a subject has a Week 28 visit performed based on the analysis visit window but androstenedione was not collected at this visit (ie, missed hormone labs), then the analysis visit date from the collection of the safety labs will be used instead for determining the Week 28 glucocorticoid total daily dose. If both hormone and safety labs were missed at the visit, then the vital signs assessment and its respective Week 28 analysis visit date will be used for determining the glucocorticoid total daily dose. The same methodology described above will be used to determine the glucocorticoid total daily dose from the eCRF at each of the other intermediate visits.

Table 4 includes the analysis visit windows for all assessments, with the exception of those assessments that have a broader window due to more infrequent assessments (ie, every 6-7 months). These more-infrequent assessments include measurements of bone age (via x-ray) and TARTs (via testicular ultrasound). These assessments will use the analysis visit windows defined in Table 6. Table 5 includes the analysis visit windows for subjects who discontinue from study drug prior to OL period or OLE and therefore do not have a first dose date in the OL period or OLE.

Scheduled Visit	Target Study Day	Analysis Window (Study Day Range)
Week 4	28	2 to 43
Week 8	56	44 to 70
Week 12	84	71 to 98

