### 9.4.2. Glucocorticoid Daily Dose

The second key secondary endpoint is the percent change from baseline in glucocorticoid daily dose (in hydrocortisone dose equivalents adjusted for BSA [mg/m^2/day]) at Week 28, while Week 28 serum and rost endione is  $\leq 120\%$  of the baseline value or  $\leq ULN$ , according to sex and either age (for Tanner stage 1) or pubertal stage (for Tanner stages 2 to 5). Glucocorticoid daily dose will be calculated at baseline (as defined in Section 6.3.1) and at Week 28 using the doses reported on the glucocorticoid medications eCRF (see details in Section 6.7 regarding mapping of the glucocorticoid medication to Week 28). Glucocorticoids other than hydrocortisone (ie, methylprednisolone, prednisolone, and prednisone) will be converted to hydrocortisone equivalents using an equivalency ratio as described in Section 6.6. BSA will be calculated using the DuBois formula (Section 7.3). The calculation of glucocorticoid dose in hydrocortisone equivalents adjusted for BSA at Day 1 and Week 28 will be based on height and weight measurements at Day 1 and Week 28, respectively. If glucocorticoid dosing alternates over the course of two consecutive days, then the average of the glucocorticoid dose on those days will be used to calculate the glucocorticoid daily dose. If glucocorticoid dosing alternates between weekdays and weekends (or another weekly regimen that varies by day of the week), then the average daily dose will be calculated as the sum of the glucocorticoid doses over the 7-day period divided by 7.

The serum androstenedione values at baseline and Week 28 to be used in the assessment of androstenedione "control" is defined in Section 6.3.5.

Subjects who have a decrease in glucocorticoid daily dose at Week 28 and who are not able to maintain their serum androstenedione at Week 28 at  $\leq 120\%$  of their baseline value or  $\leq ULN$  for sex and either age (for Tanner stage 1) or pubertal stage (for Tanner stages 2 to 5) will be considered to have a 0 percent change from baseline in the glucocorticoid daily dose at Week 28. Subjects with an increase in glucocorticoid daily dose at Week 28 will have their observed glucocorticoid daily dose value used regardless of androstenedione control. Subjects who are missing glucocorticoid dose at Week 28 and serum androstenedione at all timepoints at the Week 28 visit will have their data imputed through the multiple imputation procedure described in Section 17.2.

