## 17.3. Implementation of Tipping Point Analysis for the Primary Endpoint

A tipping point sensitivity analysis will be performed to assess the robustness of the missing data assumptions for the primary endpoint. The following steps will be taken to implement the tipping point analysis:

- 1) For the 100 imputed datasets created (as described in Section 17.1), if a subject was originally missing a Week 4 androstenedione value, add *delta* (see rules below) to the imputed Week 4 androstenedione value. Calculate the change from baseline to Week 4 in androstenedione for all subjects:
  - If Week 4 androstenedione is non-missing: change from baseline = Week 4 androstenedione value baseline androstenedione value;
  - If Week 4 androstenedione is missing and the subject is in either the crinecerfont treatment group or placebo treatment group: change from baseline = Week 4 delta-adjusted imputed androstenedione value baseline androstenedione value.
- 2) Analyze the change from baseline to Week 4 in androstenedione in each of the 100 imputed datasets using ANCOVA (as specified Section 9.2.1) using PROC MIXED. Use

PROC MIANALYZE to combine the results and obtain the LS mean statistics (within treatment, and treatment differences).

3) If the p-value in the previous step was not significant (ie, >0.05), then no additional analyses are needed. If the p-value was significant, repeat the previous steps using the next values of *delta*. Continue to do this until significance is lost, or all combinations of deltas (defined for each treatment group) have been analyzed.

The following rules will be used for defining *delta*:

- The initial delta will be = 0 (ie, an analysis of the original, multiply imputed datasets)
- For subjects in the crinecerfont treatment group, the second delta will be = 0.1745 nmol/L. If this is significant, continue to increase delta by 0.1745 until significance is lost.
- For subjects in the placebo treatment group, the second delta will be = -0.1745 nmol/L. Delta will be decreased by 0.1745 until significance is lost.

Delta may be adjusted to approach insignificance faster due to the wide range of values.

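### SAP Table 3 gives two inconsistent upper limits for androstenedione in Tanner IV–V girls: 220 ng/dL converts to 7.678 nmol/L, but 7.6678 is printed

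*SAP*

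**What the plan says.** SAP Section 6.5, Table 3, lists each androstenedione limit in conventional and SI units, with the factor "nmol/L: x 0.0349". The row for girls in the two latest pubertal stages reads "Tanner Stages IV-V: 73-220 ng/dL; 2.5477-7.6678 nmol/L". Section 6.5 takes the ranges from the laboratory manual, applies them wherever a reference range is used, and bases double-blind analyses on the Day 1 Tanner stage.

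The upper limit of normal (ULN) feeds the second key secondary endpoint in SAP Section 4.2, the percent change in glucocorticoid dose "while Week 28 serum androstenedione is ≤120% of the baseline value or ≤ ULN". The two control conditions are alternatives. Under Section 9.4.2, subjects with a reduced dose "who are not able to maintain their serum androstenedione at Week 28" within these bounds receive a percent change of 0. Section 6.7 states the same pair of conditions: "subjects who do not maintain androstenedione control and have a decrease from baseline in glucocorticoid total daily dose will have their percent change from baseline" set to 0. A raised dose is exempt: "Subjects with an increase in glucocorticoid daily dose at Week 28 will have their observed" dose used, whatever the androstenedione result.

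The SAP does not say which unit column is used for the ULN comparison. The tipping-point analysis in Section 17.3 works in SI units: "the second delta will be = 0.1745 nmol/L".

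**The concern.** The two columns of one row should describe the same cut-off, and here they do not. The cut-off is a decision threshold. It helps decide whether a dose reduction counts in the third test of the fixed sequence (SAP Section 9.1) and whether a subject can be a responder on the physiologic-dose endpoint (Section 9.5.1). Two programmers working from different columns could classify the same Week 28 result differently. Week 28 androstenedione is also multiply imputed on a continuous scale and then tested for control (Section 17.2), so the disputed band is not confined to values a laboratory would report.

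**Working it through.** **Inputs.** Factor 0.0349, the limits 73 and 220 ng/dL and the printed 2.5477 and 7.6678 nmol/L (SAP Table 3); the control and zero rules (SAP Sections 4.2, 6.7 and 9.4.2); the entry criterion that androstenedione exceed the midpoint of the reference range (Protocol Section 8.1); planned arm sizes of 54 and 27 (SAP Section 3.3).

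**1. The factor works elsewhere.**
- Lower limit, same row: 73 × 0.0349 = 2.5477, as printed.
- A close neighbour, girls aged 14, "14 years: 42-221 ng/dL; 1.4658-7.7129 nmol/L": 221 × 0.0349 = 7.7129, as printed.

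**2. The entry in question.**
- 220 × 0.0349 = 7.678, against 7.6678 printed.
- Difference: 7.678 − 7.6678 = 0.0102 nmol/L, and 0.0102 / 7.678 = 0.13%.
- Back-conversion: 7.6678 / 0.0349 = 219.71 ng/dL.
- Other factors do not rescue the printed value: 0.03492 gives 7.6824, 0.034916 gives 7.6815, 0.03485 gives 7.6670 and 0.0347 gives 7.6340.

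**3. The rest of the table.** Of the 60 androstenedione limits, 58 reproduce exactly. The lower limit for girls aged 15 is a rounding matter (46 × 0.0349 = 1.6054, printed 1.605). The remaining one is the entry above. All 17-OHP limits (× 0.0303) and testosterone limits (× 0.0347) reproduce.

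**4. When the error changes a classification.** Take a Week 28 value of 220 ng/dL (7.678 nmol/L). The ULN arm passes in ng/dL and fails against the printed SI limit. The 120% arm passes for any baseline of at least 220 / 1.2 = 183.33 ng/dL.

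| Baseline (ng/dL) | Tested in ng/dL | Tested in nmol/L, 7.6678 | Tested in nmol/L, 7.678 |
|---|---|---|---|
| 147, 160, 180, 183 | controlled | not controlled | controlled |
| 184, 200, 220, 300, 500 | controlled | controlled | controlled |

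The entry midpoint for this row is (73 + 220) / 2 = 146.5 ng/dL. Baselines between that and 183.3 are therefore possible, but the window is narrow. The Week 28 band is above 219.71 and up to 220 ng/dL. If results are reported in whole ng/dL (an assumption), it contains only the value 220.

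**5. Size if one girl is affected.** Zeroing a reduction of R percent moves the unadjusted arm mean by R/54 (crinecerfont) or R/27 (placebo). As an illustration, a fall from the entry threshold of 12 mg/m²/day to 10 or 8 is a reduction of 2/12 = 16.7% or 4/12 = 33.3%. That moves the mean by 0.31 to 0.62 percentage points on crinecerfont, or 0.62 to 1.23 on placebo. A higher starting dose would give a larger R.

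**The case against.** The strongest reply is that this is a one-digit slip with almost no reach.

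- **Several conditions must coincide.** The subject must be a girl at Tanner IV–V on Day 1, with a Week 28 value inside a 0.29 ng/dL band, a baseline below about 183 ng/dL and a reduced dose, and the comparison must be run in nmol/L. This stands, and it limits the point to a correction of the table.
- **The governing unit is unknown.** The nmol/L delta suggests SI units, but 0.1745 is exactly 5 ng/dL × 0.0349, and the 17-OHP delta of 15.15 nmol/L is exactly 500 ng/dL × 0.0303. Both look like round ng/dL figures that were converted. The sample-size section also quotes androstenedione in ng/dL. This stands: SI use is plausible, not established.
- **The extra digit may come from the reading of the PDF.** This cannot be excluded, since the available text has garbled runs elsewhere. The other androstenedione limits read cleanly against the factor, which makes it less likely but does not settle it. The laboratory manual is not available here either.
- **Supplementary analyses already vary the rule.** Section 9.4.2.2 repeats the analysis at 150% and 180% of baseline and without zeroing. At 150%, a value of 220 passes for any baseline of at least 220 / 1.5 = 146.7 ng/dL, close to the entry midpoint. These analyses would show little sensitivity, but they do not repair the primary definition.

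None of this removes the mismatch between the two columns.

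**Conclusion.** The SI entry is wrong as written, by the SAP's own factor. Confidence in the conversion is high, subject to a look at the source page. The practical effect on the second key secondary endpoint and on the responder endpoint is expected to be nil or one subject.

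Two stronger readings are tempting, and the documents support neither. A reader might infer that every girl at exactly 220 ng/dL loses her dose reduction. She does not, because the control conditions are alternatives and the zero rule also needs a dose decrease. A reader might also infer that the faulty figure is the one that will be programmed. The SAP names no governing column, so this remains a possibility.

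The point merits action only because two values for one pre-specified cut-off in a multiplicity-controlled endpoint are easily avoided.

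**What to change.** Check the source page of Table 3 and the laboratory manual. If the manual confirms 220 ng/dL, change 7.6678 to 7.678 nmol/L. Add one sentence to SAP Section 6.5 stating which unit column governs all ULN comparisons, including those on imputed values. With 7.678 in place, a result of 220 ng/dL meets the limit in either unit.

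The cost is one number and one sentence. No method, data collection or sample-size change is involved. If programs already exist, confirm which limit they use and record it.

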## 6.6. Derived and Transformed Data

Change from baseline is calculated as the postbaseline value minus the baseline value; a negative value will represent a decrease at the postbaseline visit. Percent change from baseline is calculated as: change from baseline/baseline value  $\times$  100. If either the baseline or postbaseline value is missing, the change from baseline and/or percent change from baseline will also be missing. The percent change from baseline will also be missing if the baseline value is equal to zero.

For the purpose of analysis, glucocorticoids other than hydrocortisone (ie, methylprednisolone, prednisolone, and prednisone) will be converted to hydrocortisone equivalents using an equivalency ratio of 4 (eg, 1 mg prednisone = 4 mg hydrocortisone). While dexamethasone is excluded and thus subjects are not expected to be taking dexamethasone at the time of randomization, an equivalency ratio of 60 will be used to convert dexamethasone to hydrocortisone equivalents (eg, 1 mg dexamethasone = 60 mg hydrocortisone) if dexamethasone is added to the subject's glucocorticoid regimen during the study.

With the exception of pharmacokinetic concentration data, all below the lower limit of quantification (BLQ) values will be set equal to the BLQ value in all summaries and all above the upper limit of quantification (ULQ) values will be set equal to the ULQ value in all summaries. For pharmacokinetic concentration data, all BLQ values (crinecerfont < 5.00 ng/mL; metabolites < 0.500 ng/mL) will be set equal to zero (0) in the plasma concentration summaries.

The second key secondary endpoint of percent change from baseline in glucocorticoid daily dose at Week 28 is based on the glucocorticoid concomitant medications eCRF. The method of collecting concomitant medication data involves entering a start date and stop date for each medication, unless it is ongoing, in which case the "Ongoing?" field is marked as "yes." This differs from assessments that are collected discretely at visits. Additionally, the androstenedione values collected at the Week 28 visit are a critical component to the assessment of this endpoint as subjects who do not maintain androstenedione control and have a decrease from baseline in glucocorticoid total daily dose will have their percent change from baseline value in glucocorticoid total daily dose set to 0. For the purposes of determining the glucocorticoid total daily dose from the eCRF at Week 28, the Week 28 visit date at which the androstenedione values were collected (based on the analysis visit mapping described below) will be used to determine the glucocorticoid dose (as of the same date) to be used for the second key secondary endpoint. If a subject has a Week 28 visit performed based on the analysis visit window but androstenedione was not collected at this visit (ie, missed hormone labs), then the analysis visit date from the collection of the safety labs will be used instead for determining the Week 28 glucocorticoid total daily dose. If both hormone and safety labs were missed at the visit, then the vital signs assessment and its respective Week 28 analysis visit date will be used for determining the glucocorticoid total daily dose. The same methodology described above will be used to determine the glucocorticoid total daily dose from the eCRF at each of the other intermediate visits.

Table 4 includes the analysis visit windows for all assessments, with the exception of those assessments that have a broader window due to more infrequent assessments (ie, every 6-7 months). These more-infrequent assessments include measurements of bone age (via x-ray) and TARTs (via testicular ultrasound). These assessments will use the analysis visit windows defined in Table 6. Table 5 includes the analysis visit windows for subjects who discontinue from study drug prior to OL period or OLE and therefore do not have a first dose date in the OL period or OLE.

Scheduled Visit	Target Study Day	Analysis Window (Study Day Range)
Week 4	28	2 to 43
Week 8	56	44 to 70
Week 12	84	71 to 98
Week 16	112	99 to 126
Week 20	140	127 to 168
Week 28	196	169 to (first dose date in OL period)
Week 32	224	(First dose date in OL +1) to 238
Week 36	252	239 to 266
Week 40	280	267 to 294
Week 44	308	295 to 336
Week 52	364	337 to (first dose date in OLE or Week 56)

